ready mode) powers the device; the Start/Stop button controls UVA emission; and, status display lights (Red- Internal error, yellow-UV emission, Green-Device is powered, but no UV emission) indicate the status of the UV-X™ device. A battery operated ***UV Light detector***, with a built-in low battery warning, is used to check the UV light irradiation in the treatment plane before patient treatment. The UV Light detector consists of a ***Sensor Probe and an indicator***. The ***Sensor Probe Adapter*** with a Sensor Probe is permanently mounted to the UV-light illumination system to shield the beam aperture and should only be removed for treatment.

Riboflavin Ophthalmic Solution

The riboflavin ophthalmic solution is covered under IND (redacted).

Objectives

The primary objective of this study is to evaluate two riboflavin-dosing regimens for corneal collagen cross-linking to slow the progressive changes in corneal curvature in eyes with progressive keratoconus or post refractive ectasia.

Efficacy and Safety

The primary efficacy outcome measure is change in corneal curvature, as measured by maximum keratometry (Kmax). Secondary efficacy measurements will include: pachymetry, corrected distance acuity (CDA), and manifest refraction. Safety assessments will mean reporting any adverse events. All subjects will be evaluated at baseline, Day 1, Week 1 and 3 and 6 months after treatment with vision and intraocular pressure assessed at each visit.

Ophthalmic medical records after subjects exit the study will be retrospectively reviewed to assess visual changes and incidence of any subsequent ocular interventions.

Patient Population

Six hundred patients will be enrolled in the study.

Inclusion Criteria:

Subjects who have one or both eyes that meet all of the following criteria will be considered candidates for this treatment:

1. 10 years of age or older
2. Having documented ectasia on topography or tomography after previous refractive surgery OR documented keratoconus on topography or tomography. Subjects > 32 years old who have not had prior refractive surgery must have a diagnosis of progressive keratoconus defined as one or more of the following changes over a period of 36 months or less before randomization:

- a. An increase of ≥ 1.00 D in the steepest keratometry value (or sim K)
 - b. An increase of ≥ 1.00 D in regular astigmatism evaluated by subjective manifest refraction

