If a person not of age of legal consent (18), but who is at least 10 years of age meets all inclusion/exclusion criteria for the study, parents will be given a copy of the consent form and will be given time to read it, ask any questions of the investigator and staff, and explain it to the underage subject. The parent will then determine whether the subject voluntarily decides to participate in the research. The minor will sign the consent with the parent providing assent.

Decisionally Impaired:

All subjects will be evaluated for capacity to consent through the use of the Cornea Research Foundation of America Evaluation to Sign a Consent Form. Any subjects who answer all questions satisfactorily will be permitted to provide informed consent. If the enrolling physician or designated staff member determines that a potential subject is not competent to provide a research informed consent, it will be determined whether or not the subject has a Legally Authorized Representative (LAR). If the subject does not have a LAR, they will not be permitted to enter the study. If the potential subject has a LAR, both the subject and LAR will be given a copy of the consent form and will be given time to read it and ask any questions of the investigator and staff. The LAR will then be given time to explain it to the subject. The subject will sign the consent with the LAR providing assent.

Pregnant Women:

Pregnant women will not be enrolled into this study because hormonal changes during pregnancy can sometimes temporarily alter the shape of the cornea.

Examination Schedule:

The patients will be followed to 6 months. The following examination schedule will be followed:

- Preoperative (-60 to day 0; any routine exam procedures that we performed within 60 days of study enrollment do not have to be repeated at the screening visit)
- Operative (Day 0)
- Day 1 (1-3 days)
- Week 1 or duration to healing of epithelium
- Month 3 (7 to 16 weeks)
- Month 6 (16 to 40 weeks)

Screening Eye Examination:

Potential candidates will undergo a complete eye examination to determine their eligibility for treatment. A complete ocular history, medical history and medication history will be obtained. The complete eye examination and ocular history will include:

- History of contact lens wear

- Family history of keratoconus
- History of eye rubbing
- History of refractive surgery
- UCVA (distance)
- BSCVA (distance)
- Manifest refraction
- Pentacam analysis

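### The protocol assigns the consent signature to minors and to subjects judged not competent, and assent to the parent or representative, against its own statements about who can consent

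*Protocol*

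**What the plan says.** Inclusion criterion 1 of the protocol admits subjects "10 years of age or older", so minors are expressly eligible.

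Under Vulnerable Populations, the Minors paragraph applies "If a person not of age of legal consent (18), but who is at least 10 years of age". The parents receive the form, read it, ask questions and explain it to the minor. Then: "The parent will then determine whether the subject voluntarily decides to participate in the research". The paragraph closes: "The minor will sign the consent with the parent providing assent".

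The Decisionally Impaired paragraph sets a capacity evaluation: "Any subjects who answer all questions satisfactorily will be permitted to provide informed consent". It then takes the case in which the physician or designated staff member "determines that a potential subject is not competent to provide a research informed consent". For that person, "If the subject does not have a LAR, they will not be permitted to enter the study". Where there is a LAR, both parties receive the form and the LAR explains it to the subject. The paragraph closes: "The subject will sign the consent with the LAR providing assent".

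**The concern.** Each paragraph first states that a person lacks the standing or the capacity to consent. It then names that same person as the signer of the consent and gives the parent or LAR the role of assent. On the protocol's own terms the two roles are exchanged.

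What is at stake is who authorises treatment. The procedure removes corneal epithelium and irradiates the eye for 30 minutes, and the Informed Consent section says that the treatment is not FDA-approved. Staff who follow the text literally would obtain a consent signature from a subject aged 10 to 17, or from a subject found not competent. A monitor who checks forms against the protocol would have to accept that as correct.

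**Working it through.** No arithmetic applies. The check is to compare each statement of capacity with the signature role that follows it, and then to see whether any other section reassigns the role.

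| Group | Protocol's statement on capacity | Who signs consent | Who assents |
|---|---|---|---|
| Minors | Below the legal age of consent, 18 | The minor | The parent |
| Decisionally impaired | Found not competent to give research consent | The subject | The LAR |

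**Minors.** The person who receives the form and asks the questions is the parent, and the minor learns of it through the parent. Those steps fit a parent who consents. The closing sentence nevertheless gives the consent signature to the minor. The parent's stated decision does not fill the gap, because it concerns whether the minor is acting voluntarily and does not say that the parent authorises treatment.

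**Decisionally impaired.** Satisfactory answers to all capacity questions are the paragraph's stated route to giving consent. A person found not competent has not met that condition. Making a LAR a condition of entry makes sense only if someone else is needed to authorise participation, yet the closing sentence returns the consent signature to the subject. The paragraph speaks of a potential subject and is not limited to adults.

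**Other sections of the protocol.**

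- Inclusion criterion 5 requires a signed written consent but does not say by whom.
- The Treatment section has staff confirm before treatment that a consent is present, again without naming the signer.
- The Informed Consent section has every subject provide written consent. It mentions a guardian only as a person to whom the surgeon may explain the treatment.
- The SAP does not address consent.

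None of these gives the consenting role to a parent or LAR. The Informed Consent section, read literally, reinforces the contradiction. The same exchange of roles closes both paragraphs, so it cannot be put down to a slip in a single sentence.

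**The case against.** The strongest answer is that this is a labelling error in a procedure that already needs two parties. The parent reads the form, asks questions, explains it and judges whether the minor's decision is voluntary. An impaired subject without a LAR cannot enter, and a LAR receives the form and explains it. The Informed Consent section places the process under 21 CFR Part 50 and mentions guardians, and the Institutional Review Board approves the consent form and reviews it annually. The form itself is not among the documents reviewed and may have the right signature lines.

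Most of this stands. A reader might infer that protection has been removed, or that the consents of all such subjects are invalid. The documents do not support either inference: the parent or LAR is involved throughout, and the signature lines cannot be seen. What the objection does not do is remove the contradiction, because none of these steps names the parent or LAR as the one who consents.

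A reader might also infer a statistical cost, on the reasoning that these subjects' data could be lost. With the SAP's inputs (SD 2.7 D, margin ±0.75 D, two one-sided tests at 0.05), N completers in equal arms, and a normal approximation:

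power = 2Φ(0.75/SE − 1.645) − 1, with SE = 2.7 × √(4/N)

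- From the SAP's 510 patients with 10% loss, 459 complete and power is 81.7%. If 5% to 15% of them were excluded, 436 to 390 would remain and power would be about 79% to 73%.
- From the 600 patients in the protocol's Patient Population section with the same loss, 540 complete and power is about 89%. The same exclusions leave 513 to 459 and power of about 87% to 82%.

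The arithmetic is sound but the premises are not in the documents. Neither document gives the share of minors or represented subjects, so 5% to 15% is only assumed. Neither says that data would be excluded on this ground. Even the direction relative to 80% depends on which enrolment figure is used. No power or data-loss claim should be attached to this point.

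**Conclusion.** The contradiction is real and appears in both paragraphs. The protocol assigns formal authorisation to persons whom it describes as unable to give it, and no other section corrects this. It is an inconsistency in an operative consent rule; no design choice is at issue, and the endpoint, randomisation, sample size and analysis are not touched.

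Its reach is all subjects aged 10 to 17 and all subjects entered through a LAR, in numbers that the documents do not give. The conclusion rests on the protocol text alone. It assumes nothing about what the consent form contains or what staff have done in practice. If the signed forms already carry the parent's or LAR's consent signature, what remains is a correction of wording.

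**What to change.** 1. In the Minors paragraph, state that the parent signs the consent and the minor gives assent. Say also that the parent decides on participation, in addition to judging whether the minor is willing.
2. In the Decisionally Impaired paragraph, state that the LAR signs the consent and the subject gives assent.
3. In the Informed Consent section, extend the sentence requiring written consent from every subject so that it covers consent by a parent or LAR where the subject cannot consent.
4. Check that forms already signed for subjects under 18 and for subjects with a LAR carry the parent's or LAR's signature, and that the form's signature lines match the corrected text.

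The cost is two corrected sentences, one aligned section and a review of signed forms. No analysis changes.

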Follow-Up Visits (1 Day, 1 Week, 3 and 6 months)

A treatment flow chart summarizing the follow-up examination schedule and required procedures to be performed at each treatment visit is provided in Appendix A. All subjects will be seen at 1 day, 1 week, 3, and 6 months. If a study participant is unable to return to the study site for the 1-week exam, they may see a local doctor and efforts will be made to obtain copies of this exam.

The following will be performed at each visit unless noted otherwise.

- UCVA distance
- BSCVA distance (omit on Day 1 and Week 1)
- Manifest refraction (omit on Day 1 and Week 1)
- Pentacam measurements (omit on Day 1 and Week 1) , including
 - Pachymetry
 - Scheimpflug photography
- Corneal topography (omit on Day 1 and Week 1)
- Intraocular pressure (by Goldmann applanation tonometry (omit on Day 1)
- Slit lamp examination of the cornea, anterior chamber and lens
- Optical coherence tomography (OCT, omit on Day 1)

Reasonable effort will be made by telephone and mail to contact subjects who miss a scheduled follow-up visit.

Retreatment

Any subject who is at least 1-year post- cross-linking treatment and who shows signs of progression at two visits will be considered for retreatment. Retreated eyes will not be included in the efficacy analysis and will be dosed at 5 minute intervals during irradiation.

Fellow Eyes

Patients who, at the discretion of the investigator, could benefit from the study treatment in both eyes may have both eyes treated; however, only the first treated eye per patient will be considered for the efficacy analysis. All treated eyes will be included in the safety analysis. Fellow eyes can be treated on the same or a different day as the randomized eye; this decision will be made by the patient and the principal investigator.

Safety Monitoring

During the CXL treatment procedure, subjects will be observed closely to detect the occurrence of any adverse events or complications. On the day of treatment and at each follow-up visit, the subjects will be questioned to determine whether any adverse events might have occurred since the last examination. The presence or absence of adverse events or complications will be documented.

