**Study Number: 2010-0243**

**NCT01143389**

**Version 2, Sept 12, 2017**

### *Main Outcome Measure*

The main efficacy outcome is the change in maximum keratometry (assessed by corneal tomography) from baseline to the 6-month post-treatment examination. This will be assessed for the per-protocol population as well as the intent-to-treat (randomized) population. The last-observation-carried-forward method will be used to impute missing data for participants lost to follow-up in the intent-to-treat analysis.

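### The retreatment rule, read literally, drops a randomised eye for progression after its 6-month endpoint; limit it to outcomes after the retreatment

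*Protocol*

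**What the plan says.** **Protocol, Retreatment.** "Any subject who is at least 1-year post- cross-linking treatment and who shows signs of progression at two visits will be considered for retreatment". The next sentence begins "Retreated eyes will not be included in the efficacy analysis", and its second half sets a 5-minute dosing interval for these eyes.

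**Protocol, Fellow Eyes and Data Analysis.** Both restrict the efficacy analysis to the first treated eye of each subject. Neither makes an exception for a first treated eye that is retreated later.

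**Protocol, Randomization.** Fellow eyes, which are never randomised, are kept out of the efficacy analysis in almost the same words.

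**Protocol, Examination Schedule.** "The patients will be followed to 6 months". The Month 6 window runs from 16 to 40 weeks.

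**SAP, Main Outcome Measure.** "The main efficacy outcome is the change in maximum keratometry (assessed by corneal tomography) from baseline to the 6-month post-treatment examination". On populations: "This will be assessed for the per-protocol population as well as the intent-to-treat (randomized) population". The SAP does not define the per-protocol population, does not mention retreatment, and does not say which population governs the equivalence conclusion.

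**SAP, Secondary Efficacy Outcomes.** The t tests are specified for the per-protocol population only.

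**The concern.** A retreated eye can be the subject's randomised eye. Its primary outcome is then due before retreatment becomes possible, so the second course cannot contaminate it and there is no analytic reason to discard it. The rule as worded still removes the eye.

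Retreatment follows progression, so this is exclusion on a post-randomisation event that may be related to outcome. If one regimen fails more often and its failures already look worse at 6 months, those are the eyes removed and the observed difference shrinks. In a trial whose research hypothesis is equivalence, that error favours the hypothesis.

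The documents also leave two instructions for the same eye, one keeping it and one removing it, and do not say which prevails. Protocol version 15 is dated September 2016 and SAP version 2 September 2017, so eyes treated more than a year before the SAP could already have qualified. The number is not given.

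**Working it through.** **1. Timing.** The Month 6 window closes at 40 weeks: 40 × 7 = 280 days. Retreatment is possible from 1 year, 365 days. The gap is 365 − 280 = 85 days at least.

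**2. The plan's own figure.** Inputs from the SAP: two one-sided tests at 0.05, margin 0.75 D, SD 2.7 D, true difference 0, 80% power, 10% loss, 510 enrolled. The allocation ratio is not stated; 1:1 is assumed.

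- n per arm = 2 × 2.7² × (1.645 + 1.282)² / 0.75² = 222, so 444 evaluable and 444 / 0.9 = 494 enrolled. A t-based calculation gives 223 per arm and 496 enrolled.
- At 510 × 0.9 = 459 evaluable (229.5 per arm), SE = 2.7 × √(2/229.5) = 0.252 D. Power = 2Φ(0.75/0.252 − 1.645) − 1 = 81.7% (81.5% t-based).

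The plan's figure is reproduced closely, with 510 slightly more than needed.

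**3. Size of the shift under literal exclusion.** The retreatment rates and 6-month changes below are assumptions, except where a source is named. Suppose the remaining eyes average −1.2 D in both arms. Excluding retreated eyes then removes a true difference of

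(retreated share in worse arm − share in better arm) × (6-month change in retreated eyes − change in the rest).

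| Retreated, by arm | Change in retreated eyes | Difference removed | Share of 0.75 D |
|---|---|---|---|
| 2% v 6% | +0.60 D | 0.04 × 1.8 = 0.072 D | 10% |
| 2% v 6% | +1 D | 0.04 × 2.2 = 0.088 D | 12% |
| 2% v 6% | +2 D | 0.04 × 3.2 = 0.128 D | 17% |
| 5% v 10% | +2 D | 0.05 × 3.2 = 0.160 D | 21% |

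The +0.60 D in the first row is the 6-month steepening that the protocol's Clinical Experience section reports for untreated controls in the Australian randomised study.

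**4. Whether such shifts change the conclusion.** With all eyes kept, the chance of declaring equivalence at true difference d is Φ((0.75 − d)/SE − 1.645) − Φ((−0.75 − d)/SE + 1.645). With SE = 0.252 this is 82% at d = 0, 79% at 0.09, 76% at 0.13 and 73% at 0.16 D. These arms are equivalent by the plan's own margin, so removing such a difference raises the chance of a correct claim.

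**5. When a false claim becomes more likely.** This needs a true difference near the margin. A simulation used true mean changes of −1.00 and −0.25 D (difference 0.75 D), SD 2.7 D and about 229 eyes per arm. Eyes were dropped when a later change exceeded a threshold of 2.5 to 5.5 D, which removed about 1–10% of the better arm and 2–15% of the worse. All of these except the SD, the margin and the evaluable number are assumptions.

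| Correlation of later change with 6-month change | Difference among kept eyes | Chance of falsely declaring equivalence (nominal 5%) |
|---|---|---|
| 0 | about 0.75 D | 5% |
| 0.3 | 0.68–0.73 D | 6–9% |
| 0.6 | 0.61–0.71 D | 7–14% |
| 1.0 | 0.51–0.70 D | 8–29% |

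With equal arms, equal exclusion (4.8% each) and correlation 0.6, the difference stayed near 0 and power was about 82%.

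**The case against.** The strongest reply is that the sentence means something narrower. Its second half fixes the dosing interval, which can only describe the retreatment session: an eye randomised to 2-minute dosing did not receive 5-minute dosing the first time. The Randomization section treats fellow eyes in the same way, as a non-randomised course at a set interval kept out of efficacy. The endpoint falls due before any retreatment, and the later SAP analyses all randomised subjects and lists no retreatment exclusion. All of this stands, and the narrow reading is probably what was meant.

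It does not close the point. The fellow-eye parallel also cuts the other way, because there the phrase removes the whole eye. The SAP's silence settles the intent-to-treat analysis but not the per-protocol population, which has no definition. An analyst building that set could apply the protocol sentence as written.

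The reply is also right on size. Clinical Experience reports progression halted in all 127 eyes of one treated series, and in none of a 60-eye subset treated 3–5 years earlier, so assumed retreatment rates of 2–10% may be high. Passing the 1-year point is not enough either: progression at two visits is needed, beyond scheduled follow-up.

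A reader might infer that the plan deliberately removes failures, or that its result is biased toward equivalence. The documents support neither. They do not say that the first-treatment outcome is discarded, they keep an intent-to-treat analysis, and they give no retreatment rate. The direction is not fixed: if the arms are truly equal but retreated unequally, exclusion could create a difference and work against equivalence.

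**Conclusion.** The point holds as a conflict in the text with a conditional consequence. Followed as written, the Retreatment sentence excludes randomised eyes on a post-endpoint event and contradicts both the first-treated-eye rule and the SAP's randomised population. The practical exposure is the per-protocol population, for the primary comparison and for all secondary tests.

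Bias toward equivalence needs retreatment to be more common in the worse arm and to track the 6-month change in maximum keratometry. It is nil if later progression is unrelated to that change. Only eyes retreated before the analysis is run could be affected. Under the assumed rates the shift is 0.07 to 0.16 D, at most 21% of the margin; the true size is unknown and probably small. The higher false-equivalence rates in step 5 apply only at a true difference equal to the margin and on assumed correlations, so they show what is possible and do not estimate this trial's error rate. The correction should still be made, because a stated rule that can select on failure should not depend on the analyst choosing the kinder reading.

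**What to change.** In the protocol's Retreatment section, replace the analysis clause with wording such as: *Outcomes recorded after a retreatment do not enter the efficacy analysis; the 6-month outcome of the first randomised treatment stays in both the randomised and the per-protocol populations, whether or not the eye is later retreated.* Leave the retreatment dosing text as it is.

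In the SAP, define the per-protocol population and state that later retreatment is not a reason for exclusion from it.

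The cost is one clause in the protocol and a short addition to the SAP. No extra data are needed. Enrolment stays at 510, with about 459 evaluable and power of about 82%. If the narrow reading was already intended, nothing in the analysis changes.
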